### 786 **Treatment Groups**

787 • The Test-Run Period: All participants will use the iLet in the insulin-only configuration with  
788 Humalog or Novolog (using the iLet pigtail adapter, the iLet ready-to-fill insulin cartridge, the  
789 Contact Detach infusion set, and the Dexcom G5 CGM) in one uncontrolled 7 day period.

790 • The Pediatric Transitional Study Session: All participants will use the iLet in the insulin-only  
791 configuration with Humalog or Novolog (using the iLet pigtail adapter, the iLet ready-to-fill  
792 insulin cartridge, the Contact Detach infusion set, and the Dexcom G5 CGM)

793 • Senseonics Eversense Test Run (MGH only): 4 adults will use the iLet in the insulin-only  
794 configuration using Humalog or Novolog with the iLet pigtail adapter, the iLet ready-to-fill  
795 insulin cartridge, the Contact Detach infusion set, and the Senseonics Eversense CGM as the  
796 input to the iLet in an uncontrolled 3-day period.

797 • Adult RCT Period: Three-period, random-order, cross-over study into the following study  
798 periods:

799 ○ (1) the iLet in the insulin-only configuration using Humalog or Novolog with the iLet  
800 pigtail adapter, the iLet ready-to-fill insulin cartridge, the Contact Detach infusion set,  
801 and either the Dexcom G5 or Senseonics Eversense CGM as the input depending on

- 802 the site
- 803 ○ (2) the iLet in the insulin-only configuration using faster insulin aspart (Fiasp) in
- 804 PumpCart with the iLet pigtail adapter, the Contact Detach infusion set, and either the
- 805 Dexcom G5 or Senseonics Eversense CGM) as the input, depending on the site,
- 806 where the pharmacokinetic (PK) parameter for  $t_{max}$  used by the insulin-dosing
- 807 algorithm will be set to the same value for Fiasp as is used for Humalog and Novolog
- 808 (65 minutes)
- 809 ○ (3) UC (with the Dexcom G5 or the Senseonics Senseonics Eversense CGM
- 810 depending on the site).
- 811 • Pediatric RCT Period: Two-period, random-order, cross-over study where assignment of
- 812 study period order follows either (1) the iLet in the insulin-only configuration using Humalog
- 813 or Novolog with the iLet pigtail adapter, the iLet ready-to-fill insulin cartridge, the Contact
- 814 Detach infusion set, and the Dexcom G5 CGM) in period 1 and UC (with the Dexcom G5
- 815 CGM) in period 2 or (2) UC (with the Dexcom G5 CGM) in period 1 and the iLet in the insulin-

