### 4.1. Timing of Visits

The Initial Startup Visit, or Senseonics Eversense Insertion visit where applicable, should occur within 30 days after the screening visit. Participants in the Test Run, the Senseonics Eversense Test Run, and the Pediatric Transitional Study Session may also participate in the RCT Period. Study staff will confirm they are still eligible to participate prior to enrolling them in the RCT Period.

In the three-period Adult RCT Period, there should be a minimum of 5 days, but no more than 9 days, between a Shutdown Visit and a subsequent Startup Visit. In the two-period Pediatric RCT Period, there should be a minimum of 5 days, but no more than 9 days, between a Shutdown Visit and a subsequent Startup Visit.

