#### RCT Period

In the RCT Period, participants for whom eligibility has been verified will complete each of the following phases with the order randomly assigned:

- Adult RCT Period: (i) the iLet in the insulin-only configuration with the iLet pigtail adapter and the iLet ready-to-fill insulin cartridge, the Contact Detach infusion set, and the insulin analog that they use for their usual care (either Humalog or Novolog), (ii) the iLet in the insulin-only configuration using the iLet pigtail adapter, the Contact Detach infusion set, and faster insulin aspart (Fiasp) in PumpCart, where the pharmacokinetic (PK) parameter for  $t_{max}$  used by the insulin-dosing algorithm will be set to the same value as is used for Humalog and Novolog (65 minutes), and (iii) the participant's own usual care (UC), where each participant will wear a CGM.
  - 18 adults at Stanford will use the Dexcom G5 CGM as the input to the iLet and as the CGM during usual care. 18 adults at MGH will use the Senseonics Eversense CGM as the input to the iLet and as the CGM during usual care. All 36 adults will participate in the same three arms, regardless of CGM.

- 1241 • **Pediatric RCT Period:** (i) the iLet in the insulin-only configuration with the iLet pigtail adapter  
1242 and the iLet ready-to-fill insulin cartridge, the Contact Detach infusion set, the Dexcom G5  
1243 CGM, and the insulin analog that they use for their usual care (either Humalog or Novolog),  
1244 and (ii) the participant's own usual care (UC), where each participant will wear a Dexcom G5  
1245 CGM.  
1246

1247 The participant's randomization group assignment is determined by entering the Randomization  
1248 Visit data on the study website. The Jaeb Center will construct a Master Randomization List using  
1249 a block design.  
1250

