## CHAPTER 10: STATISTICAL CONSIDERATIONS

The approach to sample size and statistical analyses are summarized below. A detailed statistical analysis plan will be written and finalized prior to the start of the study.

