2557 the iLet pigtail adapter, and the Contact Detach infusion set) using faster insulin aspart (Fiasp), where  
2558 the pharmacokinetic (PK) parameter for  $t_{max}$  used by the insulin-dosing algorithm will be set to the same  
2559 value as is used for Humalog and Novolog (65 minutes), and (3) UC (with CGM). Each treatment period  
2560 will last 7 days and there will be approximately 7 days of wash-out in between them.

2561

2562 **10.5.2. Outcomes**

2563

2564 **10.5.2.1 Main Efficacy Outcomes**

2565

2566 All pre-specified main efficacy outcomes in adult subjects will be calculated by pooling data from  
2567 subjects enrolled at the MGH and Stanford sites (and therefore using the Senseonics Eversense and  
2568 Dexcom G5 CGMs, respectively). All reference to CGM data below refers to the CGM system that is  
2569 serving as the input to the iLet.

2570

2571 There are two primary outcome metrics (mean glucose and time  $< 54$  mg/dl) and three treatment  
2572 group comparisons [(2) BP with rapid insulin vs. (3) UC, (1) BP with analog insulin vs. (3) UC, and (2)  
2573 BP with rapid insulin vs. (1) BP with analog insulin], for a total of six statistical comparisons.

2574

2575 To preserve the overall type 1 error, a hierarchical gatekeeping testing procedure will be used. If a  
2576 comparison results in a statistically significant result ( $p < 0.05$ ), then testing will proceed to the next  
2577 one on the list in the following order:

2578

- 2578 1. Mean glucose for (2) BP with rapid insulin vs. (3) UC
- 2579 2. Time  $< 54$  mg/dl for (2) BP with rapid insulin vs. (3) UC
- 2580 3. Mean glucose for (1) BP with analog insulin vs. (3) UC
- 2581 4. Time  $< 54$  mg/dl for (1) BP with analog insulin vs. (3) UC
- 2582 5. Mean glucose for (2) BP with rapid vs. (1) BP with analog insulin
- 2583 6. Time  $< 54$  mg/dl for (2) BP with rapid vs. (1) BP with analog insulin

2584

2585 This process continues iteratively moving to the next combination down on the list until a non-  
2586 significant result ( $p \geq 0.05$ ) is observed, or all six tests are performed.

2587

2588 Regardless of the results of the hierarchical testing, summary statistics appropriate to the distribution  
2589 will be tabulated by treatment period for each metric.

2590

2591 Time  $< 54$  mg/dl and mean glucose will be computed from all available CGM data during days 3-7 for  

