2592 each one of the three treatment periods in the Adult RCT Period. The performance in the iLet periods  
2593 and the difference between the iLet periods and the usual care periods can be compared with historical  
2594 data from previous bionic pancreas trials using previous generations of hardware. If the performance of  
2595 the iLet in this study is comparable to our previous data from trials using the iPhone-based bionic  
2596 pancreas that will support the hypothesis that the iLet is an effective and safe implementation of the  
2597 bionic pancreas. All participants with at least 24 hours of CGM data during days 3-7 of any two of the  
2598 three treatments periods will be included in these analyses. Summary statistics appropriate to the  
2599 distribution for time  $< 54$  mg/dl and mean glucose will be reported for all periods; while a linear model  
2600 that accounts for correlated data from the same subject will be used to compare the treatment periods  
2601 for the Adult RCT Period as described above. From prior experience, the values for time  $< 54$  mg/dl will

2602 have a skewed distribution and for mean glucose a bell-shaped distribution, but the paired differences  
2603 may follow an approximate bell-shaped curve. Residual values for the paired differences will be  
2604 examined for an approximate normal distribution. If values are highly skewed then a rank test will be  
2605 used instead. Additional models will be run to test for any carry-over effects, by adding a treatment by  
2606 order interaction term.

2607  
2608 Scatter plots for time <54 mg/dl and for mean glucose by the three randomized treatment periods in the  
2609 Adult RCT Period will be generated. Additionally, boxplots for all three periods will be generated for both  
2610 outcomes.

2611  
2612 Assuming an effective SD of 1.0% for the pair differences between any one of the three pairwise  
2613 comparisons for time <54 mg/dl, the half width of the associated 95% confidence interval are  
2614 approximately  $\pm 0.4\%$  for N=36 and  $\pm 0.6\%$  for N=18. Similarly, assuming an effective SD of 25 mg/dl for  
2615 mean glucose, the half width of the associated 95% confidence interval are approximately  $\pm 10$  mg/dl  
2616 for N=36 and  $\pm 15$  mg/dl for N=18. Results from the Medtronic 670G Pivotal Trial were used to estimate  
2617 SD for time <54 mg/dl and data from the control period of the JDRF CGM RCT were used to estimate  

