#### 2734 **10.6.2. Outcomes**

2735 All the above Adult RCT Period outcomes and analyses will be replicated here with the exceptions that,  
2736 since there are only 2 treatment periods here (instead of 3 above). For the primary outcomes, a similar  
2737 hierarchical gatekeeping procedure as the one described above for Adult RCT Period will be used; the  
2738 list will include only two outcomes in this order:

- 2739 1. Mean glucose for (1) BP with analog insulin vs. (2) UC
- 2740 2. Time <54 mg/dl for (1) BP with analog insulin vs. (2) UC

2741

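### Read as treatment-by-sequence, the planned carry-over test is the period effect in the Pediatric RCT and contains it in the Adult RCT, so drift would be reported as carry-over (minor)

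*Combined protocol and SAP*

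**What the plan says.** For the Adult RCT, section 10.5.2.1 specifies a linear model "that accounts for correlated data from the same subject will be used to compare the treatment periods". It lists no period or sequence term. The carry-over check follows: "Additional models will be run to test for any carry-over effects, by adding a treatment by" order interaction. Section 10.6.2 carries this into the two-period Pediatric RCT: "All the above Adult RCT Period outcomes and analyses will be replicated here with the exceptions that" there are two treatment periods instead of three. The differences it goes on to describe do not touch the carry-over test.

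Chapter 10 does not define order for this term. Elsewhere the word means the randomised sequence. Section 4.3 has participants complete the "following phases with the order randomly assigned". In the section 2.2 synopsis, under Treatment Groups, the pediatric "study period order follows either (1) the iLet in the insulin-only configuration using Humalog" or Novolog first with usual care second, or the reverse.

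Chapter 10 also announces a fuller document: "A detailed statistical analysis plan will be written and finalized prior to the start of the study". That document is not part of the supplied text.

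**The concern.** A carry-over test should respond to the preceding treatment and not to calendar order. If order means sequence and the model has no period effect, any general change in glucose between periods goes into the interaction. Examples are habituation to the study, a change in routine, or sensor ageing. The report would then describe ordinary drift as carry-over, and drift in the opposite direction could hide a real carry-over. A reader of the trial report could not tell which had happened.

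**Working it through.** The plan gives no figure for this test, so there is none to reproduce. The aliasing is algebra. The flag rates are illustrations for mean glucose.

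**Inputs.** Children: N = 20, two periods, 10 per sequence assumed. Adults: N = 36, three periods; section 4.3 says only that a block design is used, so six sequences and a three-sequence Latin square are both checked. The paired SD is 25 mg/dl from section 10.5.2.1 (an adult figure, assumed for children too). Two-sided 5% level assumed. Drift sizes are assumptions. For scale, the section 1.5 table gives control minus BP differences of 159−133 = 26, 158−142 = 16, 168−137 = 31 and 162−141 = 21 mg/dl for the earlier bihormonal device.

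**Children, 2×2, order = sequence.** Let A = BP, B = UC, period effects p1 and p2, and carry-overs cA and cB into the next period.
- Mean of A−B in sequence AB: τ + p1 − p2 − cA.
- Mean of A−B in sequence BA: τ + p2 − p1 + cB.
- Treatment-by-sequence is their difference: 2(p1 − p2) − (cA + cB).
- The treatment estimate is their average: τ + (cB − cA)/2. Period cancels.

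The interaction has 1 df, period has 1 df, and adding period to the interaction adds no rank. The two are the same contrast. SE = 25·√(1/10 + 1/10) = 11.18, with 18 df. With no carry-over:
- drift 5: expectation 10, noncentrality 10/11.18 = 0.89, flagged 13.5% (11–19% for SD 30–20);
- drift 10: expectation 20, noncentrality 1.79, flagged 39.5% (29–56%).

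A 10 mg/dl BP-to-UC carry-over with no drift also has expectation 10, so it is flagged 13.5%, the same as a 5 mg/dl drift.

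**Adults, order = sequence.** There are 36 × 3 = 108 observations. Subject + treatment + treatment-by-sequence has rank 36 + 2 + 10 = 48 with six sequences and 36 + 2 + 4 = 42 with three. Adding period leaves both ranks unchanged, so the 2 period df lie inside the term. With period fitted first, the interaction falls from 10 to 8 df, or from 4 to 2. Within-subject variance is 25²/2 = 312.5. For linear drift of d per period, λ = 36·2d²/312.5:

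| d (mg/dl per period) | λ | six sequences, F(10, 60) | three sequences, F(4, 66) |
|---|---|---|---|
| 5 | 5.76 | 27% | 42% |
| 10 | 23.04 | 89% | 97% |

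With period in the model both columns return to 5%. Drift of 10 per period is 20 mg/dl across the trial, about the size of the earlier device effects, so it is an upper end.

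**Order = period position, main effect included.** Drift is absorbed. In the 2×2, however, treatment-by-period is the between-subject sequence contrast, with SE = √((4b² + 625)·0.2) for between-subject SD b. At an assumed b = 25 the SE is 25.0, and power for a 20 mg/dl carry-over is 12% (19% at b = 15, 9% at b = 35).

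**Effect of omitting period on the treatment comparison.** No bias with balanced complete data, but a larger SE. Children: √(1 + (20/19)d²/625) = 1.02 at d = 5 and 1.08 at d = 10. Adults: √(1 + 72d²/(70·312.5)) = 1.04 and 1.15.

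**The case against.** The best defence is that the defect depends on one reading of one word and on a model whose full specification lies elsewhere. Chapter 10 is a summary, a detailed plan is promised, and a period term may well be in it. This stands: the period effect is unstated, not shown to be absent. It does not remove the point, because the carry-over test is stated, sequence is the natural reading, and the other reading leaves children with a test of very low power.

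The second defence is that carry-over is handled by design. Between visits "there should be a minimum of 5 days, but no more than 9 days", the outcome discards the first two days ("mean glucose will be computed from all available CGM data during days 3-7 for" each period), and the algorithm is re-initialised from body weight at each BP start-up (sections 4.5 and 4.6). This also stands, and it makes large carry-over unlikely. A 20 mg/dl carry-over would be about as large as the earlier device effects and would have to outlast all of these, so it is as extreme as the largest drift above. These safeguards do not make the test able to separate carry-over from drift.

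A reader might cite residual long-acting insulin in MDI users as a concrete carry-over route. The documents do not support that. It comes from the participant's own regimen before a BP period (section 5.4), so it enters the BP period in both sequences and does not depend on the preceding study treatment.

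**Conclusion.** The point holds on the sequence reading, and its severity is minor. The aliasing is exact and needs no assumed numbers. The flag rates rest on assumed drift, a paired SD of 25 mg/dl, balanced sequences and, for adults, an assumed number of sequences. They cover mean glucose only; nothing was computed for time <54 mg/dl, which the plan expects to be skewed.

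A reader might infer that the primary treatment comparisons are biased. The documents do not support this. With balanced complete data the period effect cancels from the treatment contrast, and leaving it out only widens the interval. Section 10.5.2.1 does admit adults with data from two of the three periods, so completeness is not guaranteed, but the documents give no basis for sizing any effect of that. Nor do they show that drift will occur. The test is supplementary, no decision rule depends on it, and these are feasibility cross-overs with convenience samples (section 10.1). What is at stake is the interpretation of a reported carry-over result.

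**What to change.** 1. In 10.5.2.1 and 10.6.2, state treatment and period as fixed effects with within-subject correlation. Define order, and state the number of adult sequences.
2. In children, do not interpret treatment-by-sequence as a carry-over test. State that carry-over cannot be separated from period within subjects.
3. In adults, run any carry-over test only in a model that includes period. Name the term in advance (treatment-by-sequence or preceding treatment) and report it descriptively. With six sequences the choice is a trade-off; with three Latin-square sequences the two terms give the same 2-df test.

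**Cost.** This is a wording change that uses 1 df in children and 2 in adults. With no drift, the pediatric 95% half-width goes from t(19)·25/√20 = 11.70 to t(18)·25/√20 = 11.74 mg/dl, 0.4% wider. In adults the ratio t(68)/t(70) is 1.0005, under 0.1% wider.

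The adult treatment-by-sequence test also loses apparent power, part of which was nonspecific. For a 20 mg/dl carry-over into any next period after BP, it falls from 94% to 69% with six sequences and from 91% to 35% with three. At 10 mg/dl with six sequences, the two candidate terms have only 18% (treatment-by-sequence) and 35% (preceding treatment). A null result in adults should therefore not be read as evidence that carry-over is absent.

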### 754 **Major Eligibility Criteria**

755 • Clinical diagnosis of type 1 diabetes for at least 12 months

756 • HbA1c level < 11.0%

757 ○ At least 13 adult participants and 6 pediatric participants in the RCT Period must have  
758 an HbA1c level of 8–11%

759 ○ At least 13 adult participants and 6 pediatric participants in the RCT Period must have  
760 an HbA1c level < 8%

761 • Using an FDA-approved insulin therapy (including Fiasp on MDI therapy for adults, Humalog  
762 or Novolog with CSII or MDI therapy; glulisine users will be excluded)

763 ○ 18 adult participants and 10 pediatric participants must use MDI therapy to manage  
764 their diabetes

765 ○ 18 adult participants and 10 pediatric participants must use CSII therapy to manage  
766 their diabetes

767 • The Adult RCT Period will enroll participants  $\geq$  18 years old

768 ○ Approximately 9 participants in a young adult group (18–24 years old)

769 ○ Approximately 27 participants in an adult group ( $\geq$  25 years old)

770 • The Pediatric RCT Period will enroll participants 6–17 years old

771 ○ 10 participants in a pre-adolescent group (< 12 years old)

772 ○ 10 participants in an adolescent group (12–17 years old)

773

774 *Additional eligibility and exclusion criteria are listed in section 3.2*

775

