### 10.1. Sample sizes

Eight adult participants are expected to complete the Test-Run Period, 4 adults are expected to complete the Senseonics Eversense Test Run, and 36 adult participants will be enrolled in the RCT Period. 20 pediatric participants are expected to complete the Transitional Study Session and 20 pediatric participants will be enrolled in the Pediatric RCT Period. These are convenience samples not based on statistical principles.

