2522 Sensor metrics will be calculated using data from days 2-3. The Senseonics Eversense Test Run will

2523 be completed and the data will be reviewed to verify safety prior to beginning the Adult RCT Period

2524 with the Senseonics Eversense CGM as the input to the iLet.

2525

2526 **10.4. Pediatric Transitional Study Session**

2527

2528 **10.4.1. Summary**

2529 20 pediatric participants (~ 6 participants age 6–11 years at Nemours, ~ 6 participants age 12–17

2530 years at Colorado, and ~ 8 participants age 6–17 years at Stanford) will be randomly assigned to the

2531 following study periods: (1) use of iLet in the insulin-only configuration with the iLet pigtail adapter and

2532 the iLet ready-to-fill insulin cartridge, the Contact Detach infusion set, the Dexcom G5 CGM, and the

2533 insulin analog that they use for their usual care (either Humalog or Novolog), and (2) participant’s own

2534 usual care (UC) where each participant will wear a Dexcom G5 CGM. The two experimental periods

2535 will each span approximately 5 days with a washout period of ~ 3 days in between. The Pediatric

2536 Transitional Study Sessions will be completed and the data will be reviewed to verify safety prior to

2537 beginning the Pediatric RCT Period.

2538

2539 **10.4.2. Outcomes**

- 2540   • The outcomes and analyses will parallel the ones mentioned above for Test-Run Period (i.e,
- 2541    Section 10.2.2) with the exceptions:
- 2542           ○ Sensor metrics will be calculated using data from days 2–5 from each experimental
- 2543            period.
- 2544           ○ The results will be presented by both experimental periods without any formal statistical
- 2545            comparison. Summary statistics appropriate to the distribution will be given separately
- 2546            for the two experimental periods.
- 2547           ○ Questionnaires will be completed at baseline and day 5 of each experimental period.

2548

2549

2550 **10.5. Adult RCT Period**

2551

2552 **10.5.1. Summary**

2553 Forty adult participants (age  $\geq 18$  years) will be enrolled at two sites and will be randomly assigned to  
2554 the following study periods: (1) the iLet in the insulin-only configuration (with the iLet pigtail adapter, the  
2555 iLet ready-to-fill insulin cartridge, and the Contact Detach infusion set) using insulin analog that they  
2556 use for their usual care (either Humalog or Novolog), (2) the iLet in the insulin-only configuration (with  

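### The 95% confidence interval half-widths printed for the adult primary outcomes are 18–21% wider than the stated SDs and sample sizes give

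*Combined protocol and SAP*

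**What the plan says.** Section 10.5.2.1 (Main Efficacy Outcomes) has one paragraph on precision for the Adult RCT.

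- For time below 54 mg/dl it begins "Assuming an effective SD of 1.0% for the pair differences between any one of the three pairwise" comparisons and prints 95% half-widths of about 0.4% (N=36) and 0.6% (N=18).
- For mean glucose it continues "Similarly, assuming an effective SD of 25 mg/dl for" that outcome and prints about 10 mg/dl (N=36) and 15 mg/dl (N=18).
- The level is given as 95% both times, for example "mean glucose, the half width of the associated 95% confidence interval are approximately" the printed values.
- The SDs are attributed to two earlier trials.

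Section 10.1 states that "36 adult participants will be enrolled in the RCT" Period and says of all the sample sizes: "These are convenience samples not based on statistical principles". Section 10.5.1 gives a different adult number, "Forty adult participants". The precision paragraph does not say what its N=18 stands for. It matches one site, or one half of the adults by insulin method (section 2.2).

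**The concern.** The paragraph gives everything a confidence interval half-width needs: the level, the SD and N. The printed results should therefore be reproducible, and none of the four is.

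Section 10 gives no power calculation for the Adult RCT, so this paragraph is the plan's only quantitative statement of what that trial can estimate on its primary outcomes. A reader cannot tell whether to rely on the SDs or on the widths. Section 2.1 describes the study as a bridge to larger pivotal trials, and the choice would matter to anyone who reused these figures for planning. Required N scales with the square of the SD, so an SD of 30 rather than 25 mg/dl means (30/25)² = 1.44 times as many participants for the same precision.

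**Working it through.** **Inputs**, all from section 10.5.2.1: two-sided 95% level; SD 1.0 percentage point for time below 54 mg/dl; SD 25 mg/dl for mean glucose, read on the same paired basis; N=36 and N=18.

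**Formula.** Half-width = t(0.975, N−1) × SD / √N, with t = 2.030 for N=36 and 2.110 for N=18.

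- N=36: 2.030 × 1.0/6 = 0.338%; 2.030 × 25/6 = 8.46 mg/dl
- N=18: 2.110 × 1.0/4.243 = 0.497%; 2.110 × 25/4.243 = 12.43 mg/dl

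| Outcome | N | Printed | Recomputed | Printed/recomputed |
|---|---|---|---|---|
| Time <54 mg/dl | 36 | 0.4% | 0.338% | 1.18 |
| Time <54 mg/dl | 18 | 0.6% | 0.497% | 1.21 |
| Mean glucose | 36 | 10 mg/dl | 8.46 mg/dl | 1.18 |
| Mean glucose | 18 | 15 mg/dl | 12.43 mg/dl | 1.21 |

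The printed widths are the same multiples of the SD for both outcomes: 0.4/1.0 = 10/25 = 0.40 at N=36, and 0.6/1.0 = 15/25 = 0.60 at N=18. The formula gives 0.338 and 0.497. This points to one common cause.

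**Other standard readings make the gap larger** (time below 54 mg/dl at N=36 and N=18, then mean glucose likewise):

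- Normal quantile: 0.327, 0.462; 8.17, 11.55
- Linear model with assumed residual df of 70 and 34: 0.332, 0.479; 8.31, 11.98
- N=40 and 20, following the forty in section 10.5.1: 0.320, 0.468; 8.00, 11.70

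**Unstated assumptions that reach or approach the printed values:**

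- SDs of 1.2% and 30 mg/dl: 0.406, 0.597; 10.15, 14.92
- 26 and 13 evaluable participants: 0.404, 0.604; 10.10, 15.11
- 90% assurance on the half-width (upper chi-square limit for the sample SD): 0.388, 0.600; 9.70, 15.0
- 97.5% level: 0.390, 0.579; 9.76, 14.48, the last of which rounds to 14

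**Back-calculated SDs.** If the printed values are read to the nearest 0.1% and 1 mg/dl, the SDs compatible with both Ns are 1.11–1.31% and 29.2–31.0 mg/dl. The stated 1.0% and 25 mg/dl lie outside.

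**The case against.** The paragraph calls its figures approximate and prints them to one significant digit or in multiples of 5. Rounding up to the next 5 mg/dl or 0.1% turns 8.46, 12.43 and 0.338 into 10, 15 and 0.4. On that view the 18–21% compares coarse values with exact ones: read to the nearest 0.1, the printed 0.4% could be 3–33% too wide and the printed 0.6% 11–31%. This stands as a caution about the percentages, and the back-calculated SD range for mean glucose does depend on reading to the nearest 1 mg/dl. It does not rescue the paragraph, because 0.497% becomes 0.5% under any rounding to 0.1, upward rounding included.

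The text says paired differences only for the first outcome, and the mean glucose SD comes from the control period of an earlier trial. If 25 mg/dl were a per-period SD with a within-person correlation of about 0.28, the paired SD would be 25 × √(2 × 0.72) = 30 mg/dl, which gives 10.15 and 14.92. That is possible, but it cannot explain time below 54 mg/dl, where the SD is explicitly for paired differences and the excess is the same.

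The widths may instead include assurance or an allowance for missing data. With 90% assurance no printed number need be wrong; the paragraph would simply omit the assumption. Section 10.5.2.1 also admits participants with data in only two of the three periods, so a pairwise comparison could rest on fewer than 36. But the text prints N=36 and N=18 and gives neither a loss rate nor an assurance level.

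Finally, nothing operational depends on these figures, and if the SDs are right the error is conservative. Both points are correct and limit the consequence.

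**Conclusion.** The four half-widths do not follow from the level, SDs and Ns printed beside them. On a paired t-interval, the reading most favourable to the plan among the standard ones, they are 18% too wide at N=36 and 21% too wide at N=18. With a normal quantile the excess is 22% and 30%. The firmest single case is 0.6% at N=18, where the inputs give 0.497%.

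This rests on taking 25 mg/dl as a paired-difference SD, the natural sense of the sentence; the result for time below 54 mg/dl needs no such assumption. Which entry is at fault cannot be settled from the documents. If the stated SDs are right, the plan understates its precision; if the widths are right, an SD or another assumption is misstated or missing. Enrolment, hypothesis tests and safety monitoring are unaffected.

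**What to change.** Retrieve the source calculation and make the paragraph in section 10.5.2.1 consistent in one of three ways:

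1. Keep the SDs and Ns, and restate the half-widths as about 0.34% and 8.5 mg/dl (N=36) and 0.50% and 12.4 mg/dl (N=18).
2. Keep the half-widths and correct the SDs, if the source shows values near 1.2% and 30 mg/dl.
3. Keep both and state what links them: the confidence level used, the evaluable N, an assurance probability, or a per-period SD with its correlation.

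In each case, say that the mean glucose SD is for paired differences if it is, and say what N=18 represents. The cost is wording only, with no change to enrolment, tests or conduct.
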